### **13.7 Statistical Analyses for Exploratory Aim 2 (Developmental Aim with Study Refusers)**

In this exploratory aim, we will gather information on barriers to participation by comparing study participants to eligible patients who declined to enroll in this study. Sample characteristics of the women who were study-eligible but declined to participate will be analyzed descriptively (using standard statistics including means, medians, standard deviations, frequencies, and percentages). Trial refusers will be asked to take a survey and responses to items on this survey will be analyzed descriptively and presented graphically as appropriate. We will also compare the study-eligible women who refused versus enrolled in the trial on demographic and clinical variables (age, disease stage, treatment status, length of time since treatment completion) obtained during screening, and sexual concerns using independent sample t-tests, Wilcoxon tests, Chi-square tests, or Fisher's exact tests, as appropriate. Women who refused and completed the survey will also be compared to those who enrolled on race/ethnicity, which is assessed during the developmental (refuser) survey. We will also compare the study-eligible women who refused the study but did not complete the survey with those who did complete the survey on the data available on these variables.

### **13.8 Power Calculations**

Power calculations are based on Aim 1 (Primary Aim). On the patient sexual function measure, a change of 5 points would be considered clinically meaningful (scale range: 2-36,  $SD \approx 10$ ). Based on pilot data, we anticipate that the  $SD$  of the change scores will be 8.2. Using our prior IE trials to guide attrition estimates, we estimate an attrition rate of 24% at 6-month follow-up, resulting in data available from 92 analyzable couples at 6-month follow-up. We will therefore have 82% power to detect a difference of 5 points in change scores, assuming a 2-sided test with type-I error ( $\alpha$ ) of 0.05. In our breast cancer pilot study, we found a between-groups difference in change scores on patient sexual function of 10.7 at post-treatment. Based on results of similar trials, we expect some attenuation of effects by 6-month follow-up. This study is powered to detect a clinically meaningful change  $> (.5 * \text{main effect})$  through the final assessment point. In sum, the study is conservatively powered to detect an effect of the IE intervention approximately half the size obtained in the pilot trial. The sample size of 120 couples (240 participants) was selected based on these calculations.

## **14.0 Data Safety Monitoring Plan**

The PI will take responsibility for monitoring the safety of all phases of the research study. The research assistant or other study team member will report any adverse events he or she observes to their respective site PI ([name] or [name]) immediately; DUMC adverse events will also be reported to [name] within 24 hours. The study consent forms have the contact information for the study PI and the appropriate Institutional Review Board (IRB), and patients may contact her or their respective IRB at any time. The research team will keep a log tracking the number, nature, and frequency of adverse events that occur in both recruiting sites and overall. Because of the nature of the research as involving procedures without significant risk (e.g., surveys; telephone psychosocial intervention) there are unlikely to be any related adverse events. Given the minimal risk of this study, it is determined that a Data and Safety Monitoring Board is not necessary for the proposed study; this plan was approved by the NCI.

## **15.0 Adverse Events**

Because of the nature of the research as involving procedures without significant risk (e.g., surveys; telephone psychosocial intervention sessions; telephone surveys) there are unlikely to be any serious adverse events and adverse events are likely to be rare. We have conducted similar studies in the past and found the risk to be extremely low. Possible risks include feeling uncomfortable or mildly distressed during questionnaire completion or during the intervention sessions given that discussions of the breast cancer experience or of the intimate relationship can be sensitive and provoke emotional reactions. Importantly, many couples' intervention studies have been conducted by members of the study team with no significant evidence of negative effects on the participants' individual or relationship well-being. A mild emotional reaction to discussions during the intervention by the patient or partner (e.g., tearfulness) is a very common reaction to the nature of the issues discussed during a cancer-related intervention, and would therefore not be considered an adverse event. Minor experiences of boredom, fatigue or discomfort during survey completion are also generally not considered to be adverse events. All participants are informed of the very minor risks of psychological reactions possibly associated with participating in the study during the informed consent process. Adverse events include significant distress or psychological reactions that interfere with study procedures such as intervention session or survey completion (e.g., severe untreated depression, suicidal intent, or extreme marital conflict). Suicidal ideation will be assessed by an item on the PHQ-9 ("Over the last 2 weeks, how often have you been bothered by thoughts that you would be better off dead or of hurting yourself in some way?"), which is administered as part of the study surveys administered at all time points. Any response except "not at all" will be considered an adverse event given that it indicates suicidal ideation for at least several days or more, although this does not necessarily indicate that the study procedures were responsible for causing these feelings. In the case of a positive response on this item, the PI's ([name], [name]), who are both licensed psychologists, or another trained member of the team will call the participant to assess current suicidal risk and need for services and will provide referrals to mental health services, if appropriate.

Any unexpected or adverse event that occurs during data collection or study procedures will be reported to the site Principal Investigator (Drs. [name] or [name]) within 24 hours, who is responsible for documenting all adverse events as well as reporting to the appropriate site IRB, if required. DUMC adverse events will also be reported to [name] within 24 hours. The research study team will bring any questionable adverse events to the attention of the Principle Investigator, and discussions will include colleagues or members of the IRB if it is unclear whether an event qualifies as an adverse event. For participants who are experiencing significant psychological distress reactions that warrant referrals to appropriate psychological services, the study team member or research assistant alerts the Principal Investigator, who would assess the need for further services. If appropriate, the PI or a trained member of the study team will provide the participant with a referral to appropriate services. The PI ([name]) and DUMC Site PI ([name]) are licensed psychologists able to make appropriate determinations and guide treatment decisions regarding psychological and marital distress. The study team will complete training in suicide prevention and risk assessment through the Columbia Lighthouse Protocol (<https://cssrs.columbia.edu/>). FCCC and DUMC counselors are available who are trained to provide psychological support services or to make specific referrals to other psychological counseling or psychiatric services in the area as needed. Moreover, participants experiencing relationship distress extreme enough that continuation in the study is contraindicated will be referred to appropriate marital or couple therapists if necessary and recommended to discontinue participation in the study, as previously described.

The research team will keep a log of the tracking the number, nature, and frequency of adverse events as part of each phase of the research plan. In accordance with FCCC guidelines, this protocol will employ the following mechanisms for adverse event reporting: 1) alert the FCCC review committees of any and all reports of adverse events; 2) inform all members of the study team of any all reports of adverse

events. All adverse events will be reviewed annually at the time of IRB continuing review. If 3 or more serious adverse events are reported, the study team will assess potential causes of the adverse events and, if events are clearly linked to study participation, discontinue the study. If there is any lack of clarity on the part of the study team with respect to proceeding in response to study safety events, the PI will contact a regulatory expert in order to determine how to proceed appropriately.

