#### 4.4 Time Commitment for Participants and Study Schema

On average, we anticipate that participants will take about 6-8 months to complete the study from consent to post-treatment assessment. Baseline and follow-up surveys will take approximately 30 minutes to complete. We expect that consent will occur no more than 2 weeks prior to the initiation of the first intervention session, although participants can begin participation in the intervention as soon as both members of the couple complete the baseline survey. The intervention sessions are intended to be delivered at weekly intervals. However, realizing that patient and partner health or other circumstances may arise that can delay sessions, we will consider completion of all four sessions within 12 weeks of randomization to be within protocol.

Completion of the post-treatment survey by both members of the couple should occur 2-7 days after completing the last intervention. Couples will receive the final two surveys 3 and 6 months after completing the last intervention session and will be asked to complete these surveys within 2

weeks. Thus, the minimum study duration would be approximately 7 months, and the maximum study duration would be approximately 9 months. This protocol will allow for skipped survey assessments, meaning if a participant does not return his or her survey within the 2 weeks outlined above, they will not be withdrawn from the study and will be permitted to complete the remaining study surveys.

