### **13.4 Statistical Analyses for Aim 2b (Secondary; Effects of IE Intervention on Patient and Partner Relationship and Psychosocial Outcomes)**

The outcomes in Aim 2b (relationship intimacy and quality, and psychological distress assessed through depressive and anxiety symptom scales) will be assessed using identical measures in both patients and partners. Multilevel modeling (MLM) will be used to test for differences in outcomes between the IE and LHT groups over time. In our primary analysis time, treatment, and role (i.e., patient versus partner) will be treated as categorical with F-tests used to assess mean differences in outcomes. These models include all main effects and interactions among these variables. Models also include random intercepts for patients and partners, as well as the correlation between the intercepts (i.e., if a patient is high in average distress across time, is the partner also high?). Models will include a time-specific correlation between the partners' residuals (i.e., if a patient is distressed at a particular time point, is the partner also distressed at that time?). In addition to modeling the interdependence between patients and partners, MLM has the advantage of not deleting participants with missing data at some time points, thus utilizing all available data.

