
**Quality Assurance Procedures for Other Study Aspects.** First, to promote transparency, the trial will be registered on clinicaltrials.gov and a protocol paper will be published. Second, we have designed standardized procedures for every aspect of study administration, from the candidate screening process to administration of the study conditions. Third, all outcome measures have demonstrated excellent psychometric properties and have prior research supporting their appropriateness in the study population and sensitivity to interventions. Fourth, REDCap, a secure web-based application, will be

used for data collection and for randomization, with an automated procedure that limits prediction of allocation and protects masking of allocations. Finally, to facilitate unbiased data collection and analysis the following steps are taken: 1) the data analyst will conduct outcome data analyses on data in which study condition is masked; 2) outcome data collection is completed in an automated fashion using REDCap, minimizing the need for contact with participants to collect study data; 3) if needed, manual data collection will be completed by study staff for whom the participant's assignment is masked to the extent possible. On an annual basis, adverse events will be reviewed across study conditions. During the annual review of adverse events, the presence of significant between-group differences could potentially warrant unmasking of the study conditions by the study biostatistician. As with most behavioral interventions, study interventionists, intervention supervisors (site PI's), and participants are not blind to study condition.

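### Apart from the PHQ-9 suicidality item, harms are recorded passively and by unblinded staff, so non-suicidal worsening may be under-counted and the across-arm comparison is open to ascertainment bias

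*Combined protocol and SAP*

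**What the plan says.** Section 15.0 describes adverse events in two ways. The first is general: "Adverse events include significant distress or psychological reactions that interfere with study procedures such as intervention session or survey completion". Its examples are severe untreated depression, suicidal intent and extreme marital conflict. The second is specific. Any answer to the PHQ-9 suicidality item other than the lowest category "will be considered an adverse event given that it indicates suicidal ideation for at least several days or more". That item belongs to an instrument "which is administered as part of the study surveys administered at all time points", and Table 2 does not restrict it to patients.

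Section 14.0 has the research assistant or another team member report events that they observe. Section 15.0 has the site PI document events arising during data collection or study procedures. Section 16.1 says that interventionists, the site PIs as their supervisors, and participants all know the study condition.

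On the use of the log, section 16.1 says "On an annual basis, adverse events will be reviewed across study conditions", and that a significant difference between groups could lead to unmasking. Section 13 contains no adverse-event or harms analysis.

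On timing, section 4.4 says that the post-treatment survey "should occur 2-7 days after completing the last intervention" session, and that "Couples will receive the final two surveys 3 and 6 months after completing the last intervention session". Section 16.1 adds that "outcome data collection is completed in an automated fashion using REDCap, minimizing the need for contact with participants to collect study data".

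Table 2 schedules the PHQ-9, GAD-7 and DAS-7 for patients and partners at baseline, post-treatment, 3 months and 6 months (T1 to T4). Section 13.4 analyses them with multilevel models and F-tests of mean differences.

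**The concern.** A plausible harm of a couple-based sexual and relationship intervention is that some couples become more distressed or get on less well. The protocol recognises this: section 10.0 provides for leaving the study because of significant psychological or marital distress, and section 15.0 lists extreme marital conflict.

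A couple who deteriorate but still attend sessions and return surveys do not clearly meet the general description in section 15.0. Nobody is scheduled to ask them about harm, apart from the one PHQ-9 item.

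The two arms also differ in what comes up in conversation. IE sessions deal with sex, communication and intimacy; LHT sessions deal with support, sleep, stress, diet and activity. Equal therapist time does not guarantee an equal chance that relationship conflict surfaces, and those who document it know the arm.

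At stake is whether the trial can say anything reliable about harm. There is no Data and Safety Monitoring Board (section 14.0), so the across-arm review of the log carries more weight. That review has no specified method. The scales that measure these harms systematically are summarised only by means, and improvement in most couples can mask worsening in a few.

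**Working it through.** The plan gives no figure for adverse-event rates or detection, so there is none to reproduce.

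**1. Time after the last session.** Section 4.4 plans weekly sessions, so four sessions span 3 weeks from the first. It allows up to 12 weeks from randomization. The last survey comes 6 months (26 weeks) after the final session.
- Weekly sessions: 26/(26+3) = 0.90.
- 12-week limit: 26/(26+12) = 0.68.

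So 68-90% of time on study has no scheduled session contact. This is a share of time without sessions, not of time without any ascertainment.

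**2. What the PHQ-9 item covers in that period.** The item asks about the last 2 weeks. At post-treatment it reaches back over the 2-7 days since the last session. At 3 and 6 months it covers 14 days each.
- Days covered: 2+14+14 = 30 to 7+14+14 = 35, out of about 182.
- Share: 30/182 = 16% to 35/182 = 19%, before the 24% attrition that section 13.8 expects by 6 months.

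**3. What unequal detection could do.** These values are assumptions, not taken from the documents: a true event rate of 5% in both arms, 120 persons per arm (60 couples), and 50% detection in LHT.
- True events per arm: 120 × 0.05 = 6. Expected LHT count: 6 × 0.5 = 3.0.

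| Detection in IE | Expected IE count | Apparent ratio IE:LHT |
|---|---|---|
| 50% | 3.0 | 1.0 |
| 70% | 4.2 | 1.4 |
| 90% | 5.4 | 1.8 |

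With no true difference, the apparent ratio runs from 1.0 to 1.8. If detection is equal there is no bias, and nothing in the documents says which row applies. Better detection in LHT would reverse the direction.

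**4. Precision of a survey-based count.** Assume 10% v 5% worsening. The half-width is 1.96 × √[(0.10×0.90 + 0.05×0.95)/n] = 1.96 × √(0.1375/n).
- n = 60 per arm (120 couples, 1:1): 0.094, so 5 points has a CI of about -4 to +14.
- n = 46 per arm (the 92 analyzable couples of section 13.8): 0.107, so about -6 to +16.

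**The case against.** A reader might infer that section 15.0 counts only events that interfere with procedures, that all harm after session 4 is missed, that unblinded interventionists are the main observers, and that the across-arm review is therefore biased. The documents do not support any of these.

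- The text uses the word include. The PHQ-9 item counts whether or not anything is disrupted, and questionable events go to the PI and, if still unclear, to colleagues or the IRB.
- Suicidal ideation is captured from both partners, in both arms, at every survey. Patients report changes in marital status at 3 and 6 months. Reasons for drop-out are queried and compared (section 13.1), distress-related departures are tracked (section 10.0), and participants may contact the PI or IRB at any time (section 14.0).
- Section 14.0 names the research assistant or another team member as reporter. Any manual data collection is masked as far as possible.
- Therapist time is matched, every interventionist is trained in both arms, and LHT also brings both partners together on stress and the cancer experience. Bias is possible but not shown.

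It can also be said that average deterioration would show in the section 13.4 models, that the protocol regards the study as minimal risk, and that the NCI approved the plan for monitoring without a Board.

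All of this stands, and it limits the point. It does not remove it. The additional routes still rely on someone noticing or volunteering a problem, or capture only couples who separate or drop out. None measures worsening distress or relationship quality in couples who stay, and a model for means does not show how many worsened.

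**Conclusion.** The point holds in this limited form. Outside the suicidality item, the adverse events described are reactions that interfere with procedures, ascertainment is passive, and the documenting site PIs are unblinded. The log is nevertheless compared across arms, with no harms analysis in section 13. Non-suicidal harm may be under-counted, most plausibly in the 68-90% of study time after the last session, and the across-arm comparison is open to ascertainment bias of unknown direction and size.

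The ratio of 1.0 to 1.8 illustrates assumed detection rates and is not an estimate for this trial. The conclusion also assumes that no further harms question sits in the survey forms; none appears in the protocol text or in Table 2. Omitting a count of participants who worsen is not an error in the efficacy analysis. It is a gap in what the trial can report about harm, and data already being collected can narrow it.

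**What to change.** Add to section 13 a descriptive end-of-study harms table. By arm, and separately for patients and partners, give the number and percentage whose PHQ-9, GAD-7 or DAS-7 worsens from baseline by at least a threshold that the investigators fix before unmasking. Show this at T2, T3 and T4 with 95% CIs and the number of surveys returned, and report it beside the adverse-event log.

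Two limits belong in the wording. First, the table should not feed the annual review in section 16.1. These are Aim 2b outcomes, and showing them by arm during the trial would be an unplanned interim look with no Board to receive it. Second, rewording the description in section 15.0 is no substitute, because it cannot recover events that were never logged.

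The cost is one table and a paragraph of analysis text, with no new data. Some worsening will be unrelated to treatment, respondents know their arm, and couples in difficulty may not return surveys, which is why the return counts are needed. Three scales, two roles and three visits give 3 × 2 × 3 = 18 comparisons, each with a half-width of about 9 to 11 points at the assumed rates. The table should therefore be labelled descriptive, without significance tests.

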### **4.2.2 Self-Report Data Collection**

An overview of study measures and collection time points for participants, including number of items in each scale, is in **Table 2**. After consenting, patients and partners will complete outcome measures at baseline, post-intervention, 3-month follow-up, and 6-month follow-up through a web portal on their home computers using REDCap.

REDCap is a secure, web-based application that is flexible enough to be used for a wide variety of research studies, offers intuitive interfaces for data entry and real time data validation, and supports easy data manipulation with audit trails and reporting capabilities, including automated export to common statistical packages. REDCap for electronic data collection is preferred over paper and pencil administration for this study because: (1) it can be completed in less time and is therefore potentially less burdensome for participants; (2) it is less burdensome to the investigators in terms of both collection and data entry – essentially eliminating the need for by-hand data entry of self-report measures; (3) it leads to fewer human errors because it obviates the need for by-hand data entry. Participants without computer or internet access will be able to complete data collection through US Mail using paper and pencil versions of the electronic data forms, sent to the couple by a study team member. If sent through US Mail, surveys will be sent (along with consent forms, if necessary) in separate envelopes with instructions to complete these independently from one another.

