#### 4.4.3 Developmental Self-Report Survey Data (Exploratory Aim 2)

All data collected from participants in Exploratory Aim 2 (developmental survey study) will be collected using the Developmental Survey, which will be administered verbally using a standardized interview format. This verbal survey collects information on patients' reasons for lack of interest in participating, preferences for resources or programs addressing sexual/intimacy concerns, relationship length/quality, level of confidence in coping with sexual concerns, and race/ethnicity. In addition, if patients endorse the item from the screening script with regard to keeping their information from the screening, we will enter these information (e.g., age, breast cancer data) into our de-identified research files for further descriptive information about this sub-sample.

Table 2. Outcome Measures		Construct	# Items	Baseline	Session 1	Session 2	Session 3	Session 4	Post-Treatment	3-Month Follow-Up	6-Month Follow-Up
Measure											
Primary Outcome											
Female Sexual Function Index (FSFI)* 		Patient Sexual Function	19	X					X	X	X
Secondary Outcomes											
Female Sexual Function Index (FSFI)  International Index of Erectile Function (IIEF) 		Partner Sexual Function	19/15	X					X	X	X
Female Sexual Distress Scale-Revised (FSDS-R)*		Sexual distress	13	X					X	X	X
Miller Social Intimacy Scale (MSIS) 		Relationship Intimacy	17	X					X	X	X
Dyadic Adjustment Scale-7 item (DAS-7)		Relationship Quality	7	X					X	X	X
Patient Health Questionnaire-9 item (PHQ-9) 		Distress (depression)	9	X					X	X	X
Generalized Anxiety Disorder 7-item (GAD-7) 		Distress (anxiety)	7	X					X	X	X
Mediators											
Dyadic Sexual Communication Scale (DSCS) 		Sexual Communication	6	X					X		
Beliefs (self-efficacy) 		Self-Efficacy	7	X					X		
Additional Measures											
Demographic information for patient/partner		Demographic data	13/9	X							
Follow-up demographic/medical questions*		Changes to marital status/medical history	2							X	X
Self-Administered Comorbidity Questionnaire (SCQ) 		Medical comorbidity	14/15	X							

Sexual Self-View	Importance of Sexuality to Self	2 BL/ 1 FU	X					X	X	X
SexFlex Scale 	Sexual Script Flexibility	6	X					X		

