#### 4.3 Overview of Randomization and Intervention Conditions

Couples will be randomized with an allocation ratio of 1:1 to either the IE or the Educational Control (Living Healthy Together) condition with stratification by age at diagnosis ( $\leq 45$  vs.  $> 45$ ) using the age obtained from the medical record (or by the patient during screening, if age at diagnosis is not available in the medical record). The statistician ([name]) will generate the randomization sequences using an automated randomization procedure in REDCap that limits prediction of allocation and protects masking of allocations. Randomization in blocks of four will guarantee that after every four assignments the study arms will have equal numbers. Separate randomization tables will be used for FCCC, Duke, and community participants to minimize the potential for unequal randomization by site.

Randomization will occur once both members of the couple have consented, completed baseline surveys, and are scheduled for their first intervention session. Randomization will occur centrally at the primary site by a staff member uninvolved in recruitment (to reduce the potential for bias in randomizing participants onto certain conditions). Once randomized, the couple will be sent sealed study materials along with the instructions to leave the envelopes sealed until they “meet” with their interventionist for session 1. It is important to keep the study condition a secret from participants until Session 1 to reduce the chances for unequal drop-out prior to Session 1, which could occur if patients/partners are more motivated to attend sessions in one study group as opposed to the other.

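### Baseline and repeated PHQ-9 item 9 positives enter the adverse event count reviewed across conditions, with no rule to separate or de-duplicate them

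*Combined protocol and SAP*

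**What the plan says.** Section 15.0 (Adverse Events) says the ideation item belongs to the PHQ-9, "which is administered as part of the study surveys administered at all time points". Any answer other than *not at all* "will be considered an adverse event given that it indicates suicidal ideation for at least several days or more". The same sentence adds that a positive answer need not have been caused by the study.

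Section 4.2.2 gives the schedule: "patients and partners will complete outcome measures at baseline, post-intervention, 3-month follow-up, and 6-month follow-up". Table 2 marks the PHQ-9 at those four points. It has no asterisk there, so patients and partners both complete it.

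Section 4.3 fixes the order: "Randomization will occur once both members of the couple have consented, completed baseline surveys, and are scheduled for their first intervention session".

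Sections 14.0 and 15.0 call for a log of how many adverse events occur, of what kind and how often. Section 16.1 states the use: "On an annual basis, adverse events will be reviewed across study conditions". It adds that a significant difference between groups could lead the biostatistician to unmask. Section 14.0 says there is no Data and Safety Monitoring Board.

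**The concern.** A between-arm safety comparison should rest on what happens after assignment. Read as written, the rule makes a baseline positive an adverse event before the couple has an arm. Once the couple is randomised, that event can be attributed to an arm in the annual review.

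Two further gaps compound this. First, no answer is compared with the participant's own baseline, so a rise from the mildest positive category to the most severe counts the same as no change. Second, the unit of counting is not stated. If each positive survey is logged as an event, one participant with unchanged ideation contributes four events, and two such people in one arm contribute eight. A test on event counts would treat those as independent.

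What is at stake is the readability of the annual comparison. Baseline positives dilute a real difference between IE and LHT. When events are few, a chance imbalance in pre-existing ideation could look like harm or hide it. With no monitoring board, the log and the annual review carry much of the safety oversight. Item 9 is also the only adverse event that has a scored threshold and is asked of everyone on a schedule.

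**Working it through.** **1. Is the PHQ-9 really in all four surveys?** The plan states no count or share of item 9 events, so the figures to reproduce are the Table 2 item totals.

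- Patient core (FSFI 19, FSDS-R 13, MSIS 17, DAS-7 7, PHQ-9 9, GAD-7 7) = 72.
- Baseline: 72 + 6 + 7 + 13 + 14 + 2 + 6 + 8 + 19 = 147.
- Post-treatment: 72 + 6 + 7 + 1 + 6 + 8 + 3 + 4 + 8 + 14 + 5 = 134.
- 3 months: 72 + 2 + 1 + 8 + 5 = 88. 6 months: 88 + 19 = 107.
- Partner core (IIEF 15 in place of the FSFI, no FSDS-R) = 55, giving 119, 109, 61 and 80 in the same way.

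All eight totals match Table 2 with the PHQ-9 included every time. The maximum is four positive surveys per person, one of them before randomisation.

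**2. What share of positives would be at baseline?** Inputs from section 13.8: 240 participants and 24% attrition at 6 months. Attrition at the two earlier follow-ups and the item 9 positive rates are not given and are assumed here. Let *s* be the sum of the retained fractions at the three follow-ups, and *r* the baseline positive rate divided by the follow-up rate. Then

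baseline share = *r* / (*r* + *s*).

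Equal rate at every survey (*r* = 1):

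| Attrition pattern | *s* | Surveys (240 × (1 + *s*)) | Baseline share |
|---|---|---|---|
| None | 3.00 | 960 | 25.0% |
| All 24% lost at 6 months only | 2.76 | 902 | 26.6% |
| 8%, 16%, 24% | 2.52 | 845 | 28.4% |
| All 24% lost before post-treatment | 2.28 | 787 | 30.5% |

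Unequal rates, with 8%, 16%, 24% attrition:

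- *r* = 0.5: 0.5 / 3.02 = 16.6%
- *r* = 1.5: 1.5 / 4.02 = 37.3%
- *r* = 2: 2 / 4.52 = 44.2%

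Section 4.1.3 excludes patients, but does not expressly exclude partners, for suicidal ideation. If that removes every baseline positive among patients, only the 120 partners contribute at baseline and the share is 0.5 / (0.5 + *s*). This is 14.3% with no attrition and 18.0% with all loss early.

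**3. How much could this dilute a real difference?** As an illustration only, take 120 people per arm, 8%, 16%, 24% attrition, a 5% positive rate at baseline and throughout LHT, and a true 10% after baseline in IE.

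- IE, all surveys: 120 × (0.05 + 0.10 × 2.52) = 36.2
- LHT, all surveys: 120 × (0.05 + 0.05 × 2.52) = 21.1
- Ratio with baseline included: 36.2 / 21.1 = 1.72
- Ratio after baseline only: 30.2 / 15.1 = 2.0

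**4. Which other rules use the count?** The discontinuation rule in section 15.0 needs three or more *serious* adverse events, clearly linked to participation. Section 15.0 does not class an item 9 positive as serious.

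**The case against.** The strongest defence is that broad capture is deliberate. Section 15.0 does not confine adverse events to intervention effects: it lists discomfort during questionnaires among the risks, and the baseline survey is a study procedure done after consent. It keeps occurrence apart from causation. For a trial without a monitoring board that is a cautious choice, and it stands. The definition itself is not at fault.

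Second, repeat counting is not stated. A log of number and frequency fits counting occurrences, but the plan does not say that repeat positives are separate events, or that baseline positives will be pooled with later ones. This also stands: the point is that the rule allows it and nothing prevents it.

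Third, baseline positives balance between arms in expectation, unmasking is discretionary, and item 9 is held by person and time point, so a cleaner summary could be built later. All true. They limit the consequence, but they do not tell whoever conducts the annual review which count to compare.

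Fourth, taking adverse event status away from unchanged ideation would narrow the reporting that section 15.0 attaches to that status, and a rule based only on new or higher answers would miss ideation that clears and then returns. Both are right, so any remedy must leave the definition and reporting alone and must flag recurrence.

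**Conclusion.** The point holds as a gap in how adverse events are tabulated for comparison. Under the stated rule, one of the four surveys that can generate an item 9 event comes before assignment, and the annual review has no instruction to set it apart, to use the participant's own baseline, or to settle the unit of counting.

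The size depends on assumptions. The baseline share is 25% to 31% if the positive rate is constant. It is about 14% to 44% over the other scenarios shown, and reaches 2 / 4.28 = 46.7% if a doubled baseline rate is paired with all loss early. The low end applies if the patient exclusion removes baseline positives.

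Four stronger readings are tempting and are not supported:

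- That a known fraction, such as a quarter, of these events predates treatment. The documents give no item 9 rate, and 25% needs equal rates and no attrition.
- That persistent ideation *is* counted four times. The documents show only that it could be.
- That these positives could by themselves stop the trial. The trigger uses serious events only.
- That the trial cannot tell whether IE raises ideation. The answers needed are collected at every survey.

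This is a cheap improvement to safety reporting. It does not touch the primary analysis.

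**What to change.** Leave the adverse event definition, the follow-up call and the reporting of every positive answer exactly as written. Add a short rule to section 16.1, cross-referenced from section 15.0, that applies only to the annual across-condition review and the final safety summary:

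- Tabulate baseline item 9 positives separately, labelled as pre-randomisation.
- Summarise post-baseline positives per participant by coded arm, so that each person counts once within a category.
- Split them into new or higher than the participant's own baseline, and unchanged or lower.
- Flag recurrence, meaning a positive answer after an intervening negative one, even if it is no higher than baseline.

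The cost is a little more tabulation, a few derived variables from answers already in REDCap, and smaller counts in the between-arm comparison. Participants are asked nothing more, and coded arms keep the masking in section 16.1 intact.
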